### Statistical Plan

Traditional Randomized Control Trials may not be the most effective way to test the efficacy of deeply-tailored, adaptive interventions. Instead, well-conducted, properly powered clinical trials that incorporate crossover design may be more useful in investigating how to optimize/enhance an evidence-based treatment (PEERS) with the experimental adjunct/primer (CICADAS). **Our trial defines: (1) three first stage treatment options; (2) a mid-study assessment point, (3) three second stage treatment options.**

After screening and enrollment, participants complete the full battery of assessments at baseline (Week 0). At Stage 1, **48** adolescents will be randomized to a 16 weeks of CICADAS only (Arm A) vs 16 weeks of PEERS + CICADAS (Arm B) vs 16 weeks of PEERS + Active Control. In order to reduce variance, we will employ a Stratified Permuted Block Randomization Design with strata defined by sensory processing symptoms to balance the number of individuals with SPA across each trial arm. After 16 weeks, the full battery of assessments will be administered again. Arms A, B and C will receive no contact for 16 weeks. At the end of the intervention, the full battery of assessments will be administered for a third time.

### Evaluation Time Points

Week 0 –primary and secondary outcome measures are collected on all participants at baseline

Week 16 – primary and secondary outcome measures are collected on all participants

Week 32 – primary and secondary outcome measures are collected on all participants

### Primary Outcome - Feasibility

Efforts will be made to assess all participants who have completed the minimum required intervention activities: For Arm A (CICADAS only), completing at least 1 hour of NB-SCT; for Arm B (PEERS + CICADAS), completing at least one PEERS group session and 1 hour of NB-SCT; and for Arm C (PEERS + Active Control), completing at least one PEERS group session and 1 hour of games.

As the main goal of this Phase I trial is to evaluate the feasibility, acceptability and usability of the CICADAS app, we will conduct an analysis of the following primary outcome measures in all ITT-CU participants:

1. Digital assessments completion rate. We expect that  $\geq 80\%$  of participants will complete the digital assessment battery at least twice during the CICADAS intervention;
2. NB-SCT program adherence, that is automatically tracked on the back-end data portal (percentage of training sessions completed). Based on our previous studies (CLIMB, MOODIFY, WASABI) and pilot, we expect that  $\geq 70\%$  of participants will complete 20 hours of NB-SCT;
4. Reported side effects (raw score). Based on our previous findings, we expect 0 adverse events due to program use;

5. Overall program completion rate. Based on previous findings from CLIMB and from the pilot in ASD, we hypothesize full program completion in  $\geq 70\%$  study participants.

Secondary Outcome - Preliminary Efficacy

The secondary outcome measures will be collected by trained personnel blind to treatment assignment at baseline, half-way through the intervention, and immediately after the treatment for all randomized participants. Weekly measures will capture the number of initiated or reciprocated social gatherings related to or in addition to PEERS assigned social activities.

**Measures of Social Cognitive Functioning:** We designed CICADAS to improve sensory processing abnormalities and social cognition in adolescents with ASD independently and to work in conjunction with PEERS to further enhance response to treatment. Our rationale is that many individuals are unable to process accurately information that underlies social and interpersonal cues. Thus, improving social cognition via targeted training of sensory processing abnormalities should confer an advantage to participants using CICADAS in conjunction with PEERS. The ability of CICADAS to prime the brain for PEERS will be measured through a subject-specific improvement in social cognition. Social cognitive functioning will be assessed a number of ways in order to gauge gains in social skills as well as ecological validity of the intervention. One of these measures will be the PEERS-based Test of Adolescent Social Skills Knowledge (TASSK; Laugeson & Frankel, 2006), a 22-item survey that assesses the teen's knowledge about the specific social skills taught during the intervention. The TASSK is comprised of sentence stems and two possible answers. Total scores range from 0 to 22, with higher scores reflecting greater knowledge of the taught social skills. Additionally, we will include the performance-based Dynamic Affective Recognition Evaluation (DARE) test for socioemotional abilities in the participant as well as parent-report measures (SRS-2, SSIS-RS) in our outcome a battery.

The secondary statistical analysis methodology is a linear mixed model approach. First, we will investigate in the ITT population any differences in baseline demographic, characterization, outcomes variables. Any such factors that show trend level significant differences ( $p < 0.1$ ) will be noted and used as covariates in the linear mixed model analysis. We will examine the data from each outcome measure using a linear mixed model with group and time as fixed factors, and covariates as necessary from the baseline analysis. Missing data will be handled with an iterative maximum likelihood procedure to optimally estimate model parameters. The key value for significance will be the group by time interaction factor for the model. Within-group effect sizes (Cohen's  $d$ ) will be computed using the mean change scores for quantitative outcomes (end-of-treatment minus baseline) and the change score SDs.

With 48 participants fully evaluated, we will not have enough power to detect a treatment augmentation effect ascribable to CICADAS. However, data from this pilot trial will be used to power a pivotal RCT in Phase II, as they will allow to explore whether:

- a) the concurrent delivery of CICADAS and PEERS for 16 weeks (B1-B2) induces greater improvements sensory processing, cognition, symptom reduction, social skills and behaviors, as well as quality of life, compared to CICADAS only (A1-A2) or PEERS + Active Control (C1-C2) – *preliminary efficacy of CICADAS as a treatment enhancer for PEERS*;
- b) The concurrent delivery of CICADAS and PEERS for 16 weeks (B1-B2) induces greater improvements sensory processing, cognition, symptom reduction, social skills and behaviors, as well as quality of life, compared to the sequential delivery of CICADAS and PEERS (A1-A3) – *preliminary testing of CICADAS as enhancer vs primer*;
- c) improvements sensory processing, cognition, symptom reduction, social skills and behaviors, and quality of life induced by the concurrent delivery of CICADAS and PEERS (B1-B2) are sustained after 16 weeks of no contact (B2-B3) – *durability of augmentation effects*.

To verify these experimental hypotheses, we will conduct the analysis based on the pre-intervention (baseline) and post-intervention data. The criterion for statistical significance is  $p < 0.05$ . Results with  $p < 0.1$  will be described as trends.

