## General Study Design

We will employ a three-arm, active-controlled, randomized crossover trial to assess the safety and efficacy of CICADAS app in adolescents with ASD, and to evaluate its potential as a stand-alone treatment, as a primer for PEERS, or as a treatment enhancer of PEERS. We will randomize adolescents with ASD (ages 11-18) to CICADAS only, PEERS + CICADAS app, or PEERS + Active Control app.

Approximately 56 participants will be consented to ensure the successful completion of 48 participants (16 participants per treatment arm). A diagnostic interview will be performed to determine eligibility. Following inclusion and enrollment, participants will complete a set of assessments prior to the intervention to establish their baseline performance. Participants will then be randomized to the CICADAS only group (Arm A), PEERS + CICADAS app group (Arm B), or PEERS + Active Control app group (Arm C) and spend up to 16 weeks engaged in their assigned intervention. After 16 weeks, a full battery of assessments will be administered. For the next 16 weeks, Arm A will continue with PEERS only and Arms B and C will receive no treatment during this period. At the end of the intervention period, a full battery of assessments will be administered a second time to evaluate changes in performance. Finally, participants will be asked to fill out an online exit survey to rate enjoyment, usability, perceived benefits, and ease of fit into schedule.

During the first intervention period, participants assigned to the CICADAS only will complete NB-SCT exercises for 16 weeks. Participants assigned to PEERS + CICADAS will engage with the CICADAS app and complete weekly 1-hour PEERS group sessions for 16 weeks. Participants assigned to receive the PEERS + Active Control will engage in the Active Control app and complete weekly 1-hour PEERS group sessions for 16 weeks. During the second intervention period, participants assigned to receive PEERS only will complete weekly 1-hour PEERS group sessions for 16 weeks. During both intervention periods, these participants may have weekly electronic check-ins with site study personnel (as needed). The CICADAS app and the Active Control app icons, design and user experience will look the same as to not unblind the participants.

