## Sample Size Justification

Attrition rates from the ASD pilot study conducted at University of Minnesota were > 30%. This high dropout rate can be ascribed to design issues, in that: (1) the sample recruited for the pilot consisted of adolescents who were not intrinsically interested in long-term treatment options for ASD, unlike the current target (adolescents already seeking PEERS); and (2) study coordinators had not been formally trained on how to keep participants engaged in a remote cognitive training intervention. By recruiting adolescents already seeking PEERS and by rigorously training our staff, we expect retention rate for this project to be in line with those of 1) cognitive interventions delivered to adolescents with ASD; 2) PEERS groups. We project a 15% non-completion rate estimate for this study. We will recruit 56 participants to obtain 48 study completers. As the primary aim of this study is to gather information about the feasibility, acceptability and usability of this approach, the sample size of N=56 is set primarily for practical reasons and not driven by hypothesis testing. This size will, however, provide data to power a subsequent pivotal efficacy trial in Phase II, and will provide the field validation data required to submit CICADAS to the FDA as a medical device for such a trial

under the 510k de novo process. We are confident that we will meet our recruitment goals with these resources in place.

Of interest to the design of our proposed trial, despite randomization to the auditory or visual training conditions, 73.2% of participants who were assigned to the Visual condition at BL completed the training whereas only 38.5% of participants who were assigned the Auditory Condition completed the program. This highlights the importance of personalized intervention programs that take individual differences (e.g., auditory sensitivity) into consideration. In fact, several participants who chose to discontinue attributed their decision to an aversion to the auditory stimuli used in the computer programs. Baseline SCAN Competing Words Test scores were significantly related to whether individuals randomized to the Auditory or Visual NB-SCT Modules completed their training [ $F(2,23) = 6.331, p = .006$ ]. In other words, participants randomized to the Auditory NB-SCT who did not complete their program had significantly more auditory processing difficulties than those who completed the program.

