## Foreseeable Risks, Risk Management & Emergency Response

Participation in the study presents minimal risk. The probability and magnitude of harm or discomfort anticipated in this research study are not greater than those ordinarily encountered in daily life or during the performance of routine physical or psychological examinations or tests.

Serious adverse effects from prior studies of the treatments under study have not been reported. The protocol details potential risks related to study participation and includes assessments of increased risk of suicidality.

The following foreseeable risks will be discussed with potential participants during the enrollment visit, as will the following measures taken to minimize such risks:

- *Diagnostic interview and self-report measures.* Participants may feel uncomfortable or embarrassed due to sensitive questioning about their psychiatric condition and medical history during the diagnostic interview or on self-report measures. Participants will be reminded during each appointment that their participation in the study is voluntary and that as such, they are not required to complete any assessments and may skip individual questions or assessments entirely.
- *Discomfort During Assessments:* Assessments may be fatiguing for some individuals, particularly for those with persistent cognitive symptoms. To minimize this potential discomfort, breaks are encouraged and scheduled within the session. In the event that a participant appears to be under undue strain, test sessions are discontinued.
- *Lack of Assessment Feedback:* Participation in this study does not include feedback to participants on their individual assessment results. Though participants are informed of this policy during consent, some participants may find the lack of feedback to be frustrating.
- *Discomfort During Intervention/Program Use:* The following risks may be reasonably anticipated as the result of intervention and/or program use: fatigue, mood complaint, headache, tremor, eye strain, neck/shoulder discomfort, leg/hip discomfort, arm/wrist discomfort, back discomfort, headache and sleep difficulty. To minimize the fatigue participants are encouraged to sit ergonomically correctly while completing study activities on their device. The program is also designed to be entertaining and enjoyable. In addition, assessment and self-report sessions may be paused at any time and participants are encouraged to take breaks.

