### **Reporting of Serious Adverse Effects & Unanticipated Device Effects**

The CICADAS protocol has minimal risk, and previous studies of similar approaches in psychiatric populations have not reported significant adverse events arising from intervention

and program use. Additionally, computerized treatment studies using Posit Science software in healthy aging, schizophrenia, and TBI have never reported adverse events attributable to study activities. Nonetheless, to follow best practices for treatment trials in medical indications, we will employ a central Medical Research Monitor to review all unanticipated problems involving risk to participants, serious adverse events, and any participant deaths associated with the protocol, and provide an unbiased written report of the event within ten calendar days. The Medical Research Monitor will comment on the outcomes of the adverse event and relationship of the event to the protocol or test article. The Medical Research Monitor will also indicate whether they concur with the details of the report provided by the study staff member. Reports for events determined by designated study personnel, i.e. Medical Research Monitor, to be possibly or definitely related to participation, and reports of events resulting in death will be promptly forwarded to Western IRB. Further, serious adverse events attributable to study activities and/or the intervention and/or program use, will be documented and reported immediately to the Western IRB. An event that is serious must be recorded on the case record and requires expeditious handling to comply with regulatory requirements. In the event that a patient becomes ill or injured as a direct result of participation in the project, necessary medical care will be made available.

The site study coordinator and PEERS clinician will ask about any deterioration in symptoms during each contact with participants, and will be alert to any volunteered episodes of suicidality. All events of this nature will be documented on a standardized form and will be classified by the PI to their degree of seriousness and their relationship to the study protocol. Participants will be referred to appropriate clinical care should there be any concerns for safety or increasing symptoms. If deemed clinically necessary, the PI may elect to remove participants from the study if they find that it is no longer in the participant's best interests to continue participation in the study.

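### The primary side-effects outcome is set against an expectation of zero app-related adverse events, with no event definition, interval or control comparison, although the protocol anticipates minor effects of program use

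*SAP*

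**What the plan says.** The SAP (Primary Outcome - Feasibility) says it will analyse the "primary outcome measures in all ITT-CU participants". Item 4 of that list is side effects, reported as a raw score, with this benchmark: "Based on our previous findings, we expect 0 adverse events due to program use". The neighbouring items carry numeric benchmarks of at least 80% (digital assessments), 70% (adherence) and 70% (program completion). For item 4 the SAP gives no definition of an event, no attribution rule, no tolerated rate, no interval and no comparison between arms.

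The protocol (Foreseeable Risks, Risk Management & Emergency Response) says: "The following risks may be reasonably anticipated as the result of intervention and/or program use: fatigue, mood complaint, headache, tremor, eye strain". The list goes on to neck, limb and back discomfort and sleep difficulty. No rates are given.

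Four other places bear on this:

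- The protocol (General Study Design) gives one purpose of the trial as "to assess the safety and efficacy of CICADAS app in adolescents with ASD".
- The support for zero is that studies of the sponsor's software in healthy aging, schizophrenia and TBI "have never reported adverse events attributable to study activities" (Reporting of Serious Adverse Effects & Unanticipated Device Effects). None of these is an ASD population.
- In the ASD pilot, "several participants who chose to discontinue attributed their decision to an aversion to the auditory stimuli used in the computer programs" (Sample Size Justification). The number is not given.
- Appendix I collects adverse effects at V1, V3 and V4, and the Assessments section says all participants receive all assessments.

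**The concern.** One document anticipates minor effects of using the program and the other expects no adverse event from using it. Both can be true only if the anticipated effects are not adverse events in the sense of item 4. The SAP does not say so, and its own label for the item, side effects, points the other way. What the item shows therefore depends on an unwritten choice about which complaints count.

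Either choice leaves the outcome uninformative. A count that includes headache and fatigue will probably not be zero, and without a control column nobody can say how much of it is due to the app. A count that excludes them may well be zero, but with this few users zero rules out little. The trial is described as assessing safety, and the Sample Size Justification says it will supply validation data for a device submission, so the form of this result matters beyond feasibility. The protocol also has the PI classify symptom deterioration by its relationship to the study protocol, which is not the same as attribution to the app.

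**Working it through.** **Inputs**

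- Benchmark: 0 events (SAP, Primary Outcome - Feasibility, item 4).
- Users, n: 16 per arm, 48 in all (protocol, General Study Design). The SAP's detailed definition of the CICADAS-users population is those who received CICADAS with PEERS, which is Arm B, about 16. Its summary wording, randomized to CICADAS access, could take in Arms A and B, about 32.
- Per-user risk, p: not in the documents. I assume 1% to 20%, with users independent.

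**The plan's own figure.** No calculation is given for item 4. The recruitment target can be checked: 48/(1 - 0.15) = 56.5, so 57, while 48 × 1.15 = 55.2, so 56. The stated 56 is reproduced to within one participant, and 48/3 = 16 per arm.

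**If the anticipated effects count.** The chance of seeing zero is (1 - p)^n.

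| Assumed p | n = 16 | n = 32 |
|---|---|---|
| 1% | 85.1% | 72.5% |
| 2% | 72.4% | 52.4% |
| 5% | 44.0% | 19.4% |
| 10% | 18.5% | 3.4% |
| 20% | 2.8% | 0.1% |

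If one user in ten has any of the listed effects, zero is missed in about 81% of trials with 16 users and 97% with 32.

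**If they do not count and zero is seen.** The upper 95% bound on the per-user risk is 1 - 0.05^(1/n) one-sided, or 1 - 0.025^(1/n) for the two-sided exact interval.

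- n = 16: 17.1% one-sided, 20.6% two-sided.
- n = 32: 8.9% one-sided, 10.9% two-sided.
- If all 56 recruited were randomised equally, Arm B would hold 18 or 19 (56/3 = 18.7), and the one-sided bound would be 15.3% or 14.6%. The SAP, however, speaks of 48 randomised.

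For zero events to exclude a 10% risk, 29 users are needed one-sided or 36 two-sided. To exclude 5%, 59 or 72 are needed.

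**What one event would show.** For 1/16 the exact two-sided 95% interval is 0.2% to 30.2%. A raw count of 1 conveys none of that width.

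**The case against.** The strongest reply is that item 4 is a descriptive expectation in a feasibility trial whose size was not set by hypothesis testing, and that no decision depends on it. Serious events, unanticipated problems and deaths already go to a monitor who comments on their relationship to the test article, and unanticipated device effects are defined. A list of possible discomforts for discussion at enrollment can stand beside an expectation of zero attributed adverse events if the discomforts are not adverse events. The Research Monitor section does separate minor discomfort from significant risk.

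Much of this stands, and it rules out four stronger readings that a reader might infer:

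- *That zero is a pass/fail criterion which one headache would fail.* The SAP says it expects zero. It states no consequence if an event occurs.
- *That the sponsor will read zero as proof of no harm.* No section says so, and the protocol's risk section concedes that symptoms may worsen and that unknown risks may exist.
- *That the two documents flatly contradict each other.* The event is undefined, so the conflict depends on what is counted.
- *That zero is almost guaranteed once the minor effects are left out.* At 16 users, a harm with a true 5% risk gives zero in 44% of trials, and one with 8% in 26% (0.92^16). Zero is likely only when the risk is very low.

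The reply does not remove the main point. The monitor's review covers serious and unanticipated events, but it neither defines nor analyses this primary outcome. Nothing in the SAP turns the count into a proportion with an interval, or sets it beside the arm that received the same group sessions with a control app.

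**Conclusion.** The point holds as a weakness in how a primary outcome is defined and analysed. If the anticipated effects count, an app behaving as the protocol expects will probably not give zero: zero is seen in 18.5% of trials at n = 16 and 3% at n = 32, at an assumed 10% of users affected. If they do not count, zero leaves per-user risks of up to 17.1% (one-sided) or 20.6% (two-sided) unexcluded at n = 16, and 8.9% or 10.9% at n = 32.

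The bounds rest only on n, which the SAP's two descriptions of the population leave at about 16 or about 32. The chances of seeing zero rest also on assumed event rates, since the documents give none. This is worth correcting before data are seen, because it changes what the trial can say about safety. It does not affect the sample size or the efficacy comparisons.

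**What to change.** Reconcile SAP item 4 with the protocol's list of anticipated effects:

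1. Limit the zero expectation to serious or unanticipated effects related to the app, which the monitor and device-effect sections already cover. State who attributes an event to the app, and which arms form the analysis set.
2. For the anticipated effects, report the proportion of CICADAS users with each effect and with any effect, with exact 95% confidence intervals, beside the same proportions in the Active Control arm. The cleanest contrast is Arm B with Arm C, which both receive PEERS. Arm A can be shown separately. With about 16 per arm the comparison is descriptive.
3. If no event is seen, report the upper bound for the actual number of users (for 0/16, 17.1% one-sided or 20.6% two-sided) and draw no conclusion that the program causes no adverse events.

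The cost is SAP wording and one extra table from data that Appendix I already schedules, with no added burden on participants. The downside for the sponsor is a less favourable safety statement than a bare zero.

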### Treatment Arms

**Arm A:** Participants assigned to Arm A will engage in CICADAS only for the first 16 weeks of the intervention period. After the completion of the first intervention period and the mid-intervention assessment (V3) visit, these participants will then be assigned to the PEERS only group for the second 16 weeks of the intervention period.

**Arm B:** Participants assigned to Arm B will engage in PEERS + CICADAS for the first 16 weeks of the intervention period. After the completion of the first intervention period and the mid-intervention assessment (V3) visit, these participants will then be assigned to No-Contact (no active intervention) for the second 16 weeks of the intervention period.

**Arm C:** Participants assigned to Arm C will engage in PEERS + Active Control for the first 16 weeks of the intervention period. After the completion of the first intervention period and the mid-intervention assessment (V3) visit, these participants will then be assigned to No-Contact (no active intervention) for the second 16 weeks of the intervention period.

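### On the TASSK, a test of PEERS content, the three-arm interaction and the B versus A contrast would show PEERS teaching and could be read as a CICADAS effect

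*SAP*

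**What the plan says.** In the SAP paragraph on measures of social cognitive functioning, "The ability of CICADAS to prime the brain for PEERS will be measured through a subject-specific improvement in social cognition". The same paragraph then states: "One of these measures will be the PEERS-based Test of Adolescent Social Skills Knowledge". It describes this instrument as "a 22-item survey that assesses the teen's knowledge about the specific social skills taught during the intervention", and on scoring says "The TASSK is comprised of sentence stems and two possible answers" and "Total scores range from 0 to 22, with higher scores reflecting greater knowledge of the taught social skills". The performance-based DARE is added, "as well as parent-report measures (SRS-2, SSIS-RS) in our outcome a battery".

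The paragraph that follows fits a linear mixed model to each outcome, with group and time as fixed factors, and takes the group-by-time interaction as the key test. Three exploratory questions come next:

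- (a), enhancement: change in B from baseline to week 16 against the same change in A or in C.
- (b), enhancer versus primer: change in B to week 16 against change in A to week 32.
- (c), durability of B's gains.

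None of the three is tied to particular measures.

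The Protocol (Treatment Arms) says "Participants assigned to Arm A will engage in CICADAS only for the first 16 weeks of the intervention period"; PEERS follows for that arm in the second 16 weeks. Arms B and C have PEERS in the first 16 weeks, with the CICADAS app and the control app respectively. The TASSK is given at V1, V3 and V4 (Protocol, Appendix I).

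**The concern.** A test of taught content should rise in arms that have been taught and stay roughly level in an arm that has not. At V3 the three arms differ in exactly that respect. A significant TASSK interaction, or a B versus A difference, could therefore be reported as CICADAS enhancing PEERS when it shows only that PEERS teaches its curriculum. The SAP intends these data to power the Phase II trial, so a misattributed effect would carry forward into that design. In the other direction, a level TASSK in Arm A at V3 could be held against CICADAS as a primer, although Arm A had not yet been taught the content.

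**Working it through.** **1. What each TASSK contrast isolates** (exposures from Protocol, Treatment Arms)

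| Contrast | Differs in | What a TASSK difference shows |
|---|---|---|
| B v A, V1 to V3, in question (a) | PEERS; both have CICADAS | mainly PEERS teaching |
| B v C, V1 to V3, in question (a) | CICADAS v control app; both have PEERS | CICADAS added to PEERS |
| A, V1 to V3 | CICADAS only, before PEERS | no taught content yet; weak evidence on priming |
| B to V3 v A to V4, in question (b) | concurrent v sequential delivery | A's gain mixes PEERS teaching with any priming |

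No arm receives the control app followed by PEERS, so nothing in the design separates the two parts of Arm A's gain to V4.

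**2. How often PEERS timing alone gives significance at V3**

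Inputs: 16 completers per arm (Protocol, General Study Design) and p < 0.05 (SAP). Assumptions: two-sided t test, normal change scores with equal variance, a CICADAS effect of exactly zero, and the same PEERS effect d in B and C, in SDs of the V1 to V3 change. The documents give no TASSK effect or SD, so d is shown over a range.

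- Three-arm test on change. Means are 0, d, d and the grand mean is 2d/3. Squared deviations sum to 4d²/9 + d²/9 + d²/9 = 2d²/3. Noncentrality is 16 × 2d²/3 = 10.67d², with 2 and 45 df.
- B v A. Noncentrality is d × √(16/2) = 2.83d, with 30 df.

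| Assumed PEERS effect d | P(three-arm test significant) | P(B v A significant) |
|---|---|---|
| 0.5 | 27% | 28% |
| 0.8 | 61% | 59% |
| 1.0 | 81% | 78% |
| 1.5 | 99% | 98% |

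Under the same assumptions B v C is significant 5% of the time, which is the nominal rate.

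**3. What B v C can detect**

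With 16 v 16, two-sided 0.05 and 80% power, the detectable difference is (1.96 + 0.84) × √(2/16) = 0.99 SD. The SAP already says the trial lacks power for an augmentation effect.

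**4. The TASSK scale**

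The stated range reproduces: 22 items at 0 or 1 point give 0 to 22. With two answers per item, blind guessing gives a mean of 22 × 0.5 = 11 and an SD of √(22 × 0.25) = 2.35. P(15 or more) is 0.067 and P(10 or less) is 0.416. No baseline TASSK score is given, so these figures show neither a floor effect nor a bias between arms.

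**The case against.** The strongest reply is that the SAP does not score priming on the TASSK in Arm A before PEERS. It ties priming to no window and no single instrument, and its one primer contrast, question (b), runs to week 32, after Arm A's PEERS course. The Protocol background describes CICADAS as preparing the brain to learn what PEERS teaches, and on that account a TASSK taken after PEERS is a relevant readout. This stands.

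A reader might go further and infer that the TASSK cannot register priming at all, or that its expected change in Arm A before PEERS is zero. The documents do not support that. No items are shown, CICADAS includes prosody, gaze and social-memory tasks, and retesting could move the score. A reader might also infer from the guessing arithmetic that the scale is defective. It is not shown to be: a chance level of half the items belongs to any two-choice test, and the SAP states the range without any claim about sensitivity.

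Other limits on the concern also stand. The DARE, SRS-2 and SSIS-RS are modelled separately, so a level TASSK cannot mask a change on them. The TASSK enters none of the composites under Calculations from CRFs. The outcomes are secondary, and the SAP calls the comparisons exploratory.

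None of this answers the attribution problem. The interaction remains the key test for each outcome, question (a) names Arm A's change to week 16 as a comparator, and no text exempts the TASSK from either.

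**Conclusion.** The concern holds for attribution. On the TASSK, a group-by-time interaction or a B versus A difference at V3 is expected from PEERS teaching alone, and question (a) would allow it to be read as CICADAS enhancing PEERS. The chance of such a result with no CICADAS effect runs from about a quarter at d = 0.5 to near certainty at d = 1.5, given the assumptions in the working; the direction follows from the arm schedule and the instrument's description. Arm A's change to V3 is weak evidence on priming in either direction, and its change to V4 cannot separate priming from teaching.

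The problem is confined to TASSK results and leaves the primary feasibility outcomes untouched. It merits an SAP amendment before analysis. The chance score of 11 is a reporting note and not an error in the plan.

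**What to change.** Amend the SAP's outcome paragraph and its exploratory questions as follows.

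- Draw TASSK inference about CICADAS only from B versus C at V3, where both arms have had PEERS. Report the three-arm TASSK interaction, if at all, as reflecting PEERS exposure.
- Exclude the TASSK from the B versus A part of question (a) and from evidence on priming in Arm A between V1 and V3.
- Read that Arm A window on measures that do not test PEERS content: the DARE, with the SRS-2 and SSIS-RS as supportive. This is a single-arm change in about 16 participants and is open to retest effects, so it should be described as such.
- Label any comparison of Arm A's V3 to V4 TASSK gain with Arm C's V1 to V3 gain as exploratory only. The periods are not concurrent, Arm A is on a later retest, and Arm C also used the control app.
- Reconcile the SAP's Statistical Plan, which has all three arms under no contact in the second 16 weeks, with the Protocol's Treatment Arms and with question (b), both of which have Arm A receiving PEERS after CICADAS. The exploratory comparison and question (b) depend on this.
- State the chance score of 11 when TASSK results are reported.

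The cost is wording only, since the data are already scheduled at V1, V3 and V4. The downside is that fewer measures and contrasts support the CICADAS claims, and the B versus C contrast that remains on the TASSK has 80% power only for a difference of about one SD.
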